6.7 Drug accountability

Handling, preparation and administration of trial medication will be done by unblinded trial personnel. Each center will keep accurate records of the trial supplies received, stored, and dispensed, using appropriate forms. The trial supplies will be stored under appropriate conditions, locked and with restricted access.

All unused supplies and all empty and partially empty containers of trial medication will be stored until the trial closure visit has been performed and then sent for destruction. This does not apply to the used syringes as they will be discarded after dose administration. Destruction must not take place until approved by the Sponsor.

6.8 Treatment compliance

All trial medications will be prepared and administered by unblinded trial personnel.

PK assessments will support the surveillance of compliance with IMP administration.

6.9 Prior and concomitant medications

Prior glucagon exposure will be recorded in the eCRF at screening. All concomitant medications will be recorded and/or updated in the eCRF at each visit.

Subjects using any new concomitant medication resulting in fulfillment of a dosing day exclusion criterion (see Section 5.5) will be excluded from the dosing visit, but can be

rescheduled to one of the following days (1–7 days later). The dosing visit can only be rescheduled once.

6.9.1 Prohibited medications

The use of anti-coagulant treatments and medications (prescription and non-prescription) that are known to cause QT prolongation are prohibited during the course of the trial.

Within 28 days prior to dosing, the use of daily systemic beta-blockers, indomethacin, warfarin, and anticholinergic drugs is prohibited.

Within 2 weeks prior to dosing, the use of any non-prescribed systemic or topical medication (with the exception of vitamins and the occasional use of acetylsalicylic acid and paracetamol) is prohibited.

Within 48 hours prior to dosing, the use of insulin Degludec or insulin Glargine U300 are prohibited.

Within 24 hours prior to dosing, the use of long-acting insulin (e.g., insulin Glargine U100 or insulin Detemir) is prohibited.

Within 16 hours prior to dosing, the use of insulin NPH is prohibited.

Within 6 hours prior to dosing, the use of any short acting (bolus) insulin, except insulin glulisine (Apidra®) is prohibited.

During the insulin-induced hypoglycemic procedure, continuous SC insulin infusion must be stopped.

6.10 Local German requirements for insulin glulisine (Apidra®)

Insulin glulisine (Apidra®), the insulin used to induce hypoglycemia, will according to local requirements be defined as an investigational medicinal product when used at German sites. The insulin will be provided by the local sites and drug accountability will be performed according to local procedures. In contrast to the trial drug for the randomized treatment, the insulin will be administered by the blinded trial personnel via IV infusion as described in section 8.2.3.1.

7 PARAMETERS AND METHODS OF ASSESSMENT

Overall, approximately 180 mL of blood will be drawn from each subject for PK, PD, ADA, and safety laboratory assessments.

7.1 Efficacy parameters

A description of the sample handling and sample processing at the site will be included in the laboratory manuals. Validation documentation for the assays must be available prior to sample analyses. A bioanalytical report for each analysis of trial PD and PK samples will be prepared.

7.1.1 *Pharmacodynamic measurements*

The plasma glucose profile for evaluation of the primary and secondary clinical efficacy endpoints will be assessed based on plasma concentration data ($AUC_{0-30\text{min}}$) from samples collected at the dosing visit (Visit 2). The samples will be sent to the clinical laboratory and analyzed using a sensitive and validated assay for glucose measurements.

Samples will be collected pre-dose, and at 4, 6, 8, 10, 12, 15, 17, 20, 25, 30, 40, 50, 60, 75, and 90 minutes after dosing (see the schedule of procedures in [Table 3](#)). The actual time of blood sampling for evaluation of plasma glucose should not deviate from the nominal time by more than ± 30 seconds until the 20 minute collection time point and by more than ± 1 minute for the subsequent collection time points. Pre-dose is defined as within 2 minutes prior to dosing.

7.1.2 *Pharmacokinetic measurements*

The exposure to trial medication (dasiglucagon or GlucaGen) for evaluation of PK will be assessed based on plasma concentration data ($AUC_{0-90\text{ min}}$, C_{max} , t_{max}) from samples collected at the dosing visit (Visit 2).

Samples (including back-up samples) will be collected pre-dose, and at 15, 30, 35, 40, 50, 60, 90, and 120 minutes after dosing (see the schedule of procedures in [Table 3](#)). The actual time of blood sampling for exposure to trial medication should not deviate from the nominal time by more than ± 1 minute. Pre-dose is defined as within 2 minutes prior to dosing.

7.2 Safety parameters

7.2.1 *Adverse events*

The investigator is responsible for the detection and documentation of events meeting the criteria and definition of an AE or serious adverse event (SAE), as provided in this protocol. During the trial, the investigator or center staff will be responsible for reporting AEs and SAEs, as detailed in this section of the protocol.

Based on the investigator's clinical judgment it will be determined whether an AE is related to treatment and of sufficient severity to require the subject's removal from treatment or from the trial. A subject may also voluntarily withdraw from treatment due to what he or she perceives as an intolerable AE. If either of these situations arises, the subject should be under medical supervision until symptoms cease or the condition becomes stable.

7.2.1.1 *Definitions*

Adverse event

An AE is any untoward medical occurrence in a trial subject given an IMP which does not necessarily have a causal relationship with the treatment. An AE can therefore be any unfavorable and/or unintended sign (for example, an abnormal laboratory finding), symptom, or disease temporally associated with the use of an IMP, whether or not considered related to the IMP.

In this trial, only treatment-emergent adverse events (TEAEs) will be collected and reported. TEAEs are events that occur from the first trial-related activity after the subject has signed the informed consent form until the end of the post-treatment follow-up period.

AEs include:

- A clinically significant worsening of a concomitant illness.
- A clinical laboratory abnormality which is clinically significant, i.e. any abnormality that suggests a disease and/or organ toxicity and is of a severity that requires active management. Active management includes active treatment or further investigations, for example change of medicine dose or more frequent follow-up due to the abnormality.
- Hypoglycemic episodes (see Section 7.2.2).
- Injection site reactions (see Section 7.2.6).

The following should not be recorded as AEs, if recorded at screening (on the Screening Form or eCRF):

- Pre-planned procedure, unless the condition for which the procedure was planned has worsened from the first trial related activity after the subject has signed the informed consent.
- Pre-existing conditions found as a result of screening procedures (pre-existing conditions should be reported as medical history or concomitant illness).

Serious adverse event

An SAE is any untoward medical occurrence that at any dose:

- Results in death
- Is life-threatening
- Requires inpatient hospitalization or prolongation of existing hospitalization
- Results in persistent or significant disability or incapacity
- Is a congenital anomaly or birth defect
- Is medically important*

*Medical judgement must be exercised in deciding whether an AE is believed to be 'medically important'. Medically important events may not be immediately life-threatening or result in death or hospitalization but may jeopardize the subject or may require intervention to prevent one of the other outcomes listed in the definition above.

Adverse drug reaction

All noxious and unintended responses to an investigational product related to any dose should be considered adverse drug reactions. The phrase responses to an investigational product means that a causal relationship between an investigational product and an adverse event is at least a reasonable possibility, i.e. the relationship cannot be ruled out.

Suspected unexpected serious adverse reactions (SUSARs)

An AE fulfilling one of the criteria of seriousness and being assessed as related to IMP application, the nature or severity of which is not consistent with the applicable reference document (e.g. dasiglucagon Investigator's Brochure or package leaflet/Summary of Product Characteristics for GlucaGen).

Adverse event of special interest

An AESI is an event which, in the evaluation of safety, has a special focus (e.g. required by health authorities). In this trial hemodynamic changes, as defined below, are considered AESIs:

- Post-dose clinical signs, or measured vital signs, indicating a clinically significant drop in blood pressure including signs of orthostatic hypotension, vasovagal responses or bradycardia.
- Post-dose change in pulse or blood pressure considered an event of hypo- or hypertension as judged by the investigator.

Intensity of an adverse event

The maximum intensity (severity) of all AEs must be assessed by the investigator and documented. Severity should be graded when the AE outcome is known:

Mild: A type of AE that is usually transient and may require only minimal treatment or therapeutic intervention. The event does not generally interfere with usual activities of daily living.

Moderate: A type of AE that is usually alleviated with additional specific therapeutic intervention. The event interferes with usual activities of daily living, causing discomfort but poses no significant or permanent risk of harm to the subject.

Severe: A type of AE that interrupts usual activities of daily living, or significantly affects clinical status, or may require intensive therapeutic intervention.

A ‘severe’ reaction does not necessarily deem the AE as ‘serious’ and an SAE may not necessarily be ‘severe’ in nature.

Causality relationship to trial medication

The causality of each AE should be assessed by the investigator according to the following classification:

Probable: Good reason and sufficient documentation to assume a causal relationship.

Possible: A causal relationship is conceivable and cannot be dismissed.

Unlikely: The event is most likely related to etiology other than the trial product.

Not related: No relationship to trial product.

***Germany only:** The investigator should assess the causality to dasiglucagon/placebo/GlucaGen and to insulin glulisine (Apidra®) respectively. A special field applicable for Germany only will be present on the AE form in the eCRF to capture this data.*

Outcome of an adverse event

The outcome of all AEs must be assessed by the investigator and documented by his/her staff. The following definitions should be used:

Recovered/resolved:

The subject has fully recovered, or by medical or surgical treatment the condition has returned to the level observed at the first trial-related activity after the subject signed the informed consent.

Recovering/resolving:

The condition is improving and the subject is expected to recover from the event. This term is only applicable if the subject has completed the trial.

Recovered/resolved with sequelae:

The subject has recovered from the condition, but with lasting effect due to a disease, injury, treatment or procedure. If a sequela meets an SAE criterion, the AE must be reported as an SAE.

Not recovered/not resolved:

The condition of the subject has not improved and the symptoms are unchanged.

Fatal:

This term is only applicable if the subject died from a condition related to the reported AE. Outcomes of other reported AEs in a subject before he/she died should be assessed as "recovered/resolved", "recovering/resolving", "recovered/resolved with sequelae" or "not recovered/not resolved". An AE with fatal outcome must be reported as an SAE.

Unknown:

This term is only applicable if the subject is lost to follow-up.

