7.2.1.2 Collection, recording and reporting of adverse events

All events meeting the definition of an AE must be collected and reported from the first trial related activity after the subject has signed the informed consent until the end of the post-treatment follow-up period. At each contact with the center (visit or telephone, excluding visits where the subject is not seeing the investigator or his/her staff [e.g. visits

to the laboratory]) the subject must be asked about AEs. All AEs, either observed by the investigator or reported by the subject, must be recorded by the investigator and evaluated.

The investigator should record the diagnosis, if possible. If no diagnosis can be made the investigator should record each sign and symptom as individual AEs.

One single Adverse Event Form must be used per AE from start to resolution. For SAEs, the Serious Adverse Event form must also be completed. For AESIs, the AESI form must also be completed.

AE information should include the following:

- Date and time of onset and resolution
- Date and time of investigator's first information on the (S)AE
- Seriousness
- Severity
- Causal relationship with IMP
- Interruption or withdrawal of treatment during IMP administration and other measures taken
- Outcome.

All AEs are coded; details are described in the trial-specific Data Management Plan.

If an event classifies as a AESI, the investigator must tick the AESI box on the AE form and complete the AESI form. The AESI form will capture if the event was associated with any signs or symptoms and capture the highest/lowest blood pressure and pulse measured during the event. The investigator must report all AESIs to the sponsor's responsible pharmacovigilance unit (Safety CRO; see the list of trial personnel in Section 12.1) immediately (within 24 hours) after obtaining knowledge about the event.

The investigator must report initial information electronically (e.g. in PDF format) on all SAEs to the sponsor's responsible pharmacovigilance unit (Safety CRO; see the list of trial personnel in Section 12.1) immediately (within 24 hours) after obtaining knowledge about the event. The Safety CRO will inform the medical monitor and the sponsor about the reported SAEs.

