7.2.2 Hypoglycemia

Hypoglycemia will be regarded as an AE and recorded and documented on an AE form (and SAE form, if applicable).

Hypoglycemia is defined as a decline in plasma glucose to below 70 mg/dL (3.9 mmol/L). However, in the time period from initiation of the hypoglycemic clamp procedure (see Section 8.2.3.1) until 45 minutes after dosing, hypoglycemia is defined as a decline in plasma glucose to below 45 mg/dL (2.5 mmol/L).

During the dosing visit, prior to administration of the IMP, a plasma glucose value of <45 mg/dL (2.5 mmol/L) will be treated by an IV glucose solution. After administration of the IMP in the period from 8 minutes until 44 minutes after dosing, a plasma glucose value of <45 mg/dL (2.5 mmol/L) will be treated by an IV glucose solution, and if a plasma glucose value of \geq 70 mg/dL (3.9 mmol/L) is not achieved within the 45 minutes after IMP administration, IV glucose infusion will also be initiated.

If the subject experiences symptoms of hypoglycemia, a plasma glucose measurement should be taken in order to classify the event (please refer to Section 7.4.2 for additional details).

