8.2 Procedures by visit

8.2.1 *Visit 1 (screening, Day -30 to Day -3)*

Visit 1 will take place between 3 and 30 days before Visit 2, Day -1 to Day 1 (dosing day).

Informed consent can be obtained prior to or at Visit 1, however it must in any case be obtained prior to any trial related procedures. During the screening visit, the following assessments will take place:

- Informed consent (obtain or check)
- Check of subject eligibility (inclusion/exclusion criteria)
- Demography
- Body measurements
- Medical history, diabetes diagnosis, current diabetes treatment
- Concomitant illnesses
- Concomitant medications
- History of alcohol/drug abuse
- Physical examination
- Vital signs
- 12-lead ECG
- AEs
- Biochemistry, hematology, coagulation, HbA_{1c}
- Serum pregnancy test (women of childbearing potential only)
- Urinalysis
- Urine drug screen
- Alcohol breath test

Table 3 Schedule of procedures

Visit number	V1	V2	V3
Trial day	-3	-1 and 1	28
Visit type	Screening	Dosing	Follow-up
Window	-30 to -3		+5 days
Subject related information/assessments			
Informed consent	x		
Inclusion/exclusion criteria	x	x ^{1,2}	
Demography	x		
Body measurements	x		
Medical history, diabetes diagnosis, and current diabetes treatment	x		
Concomitant illnesses	x		
Concomitant medications	x	x ¹	x
History of alcohol/drug abuse	x		
Randomization		x ¹	
Withdrawal criteria		x ¹	
Dosing day exclusion criteria		x ¹	
Insulin-induced hypoglycemia		x	
Safety assessments			
Physical examination	x		x
Vital signs	x	x ³	x
12-lead ECG	x	x ⁴	x
Local tolerability		x ⁵	x
Adverse events	x	x	x
Laboratory			
Biochemistry, hematology, coagulation, HbA _{1c} (coagulation and HbA _{1c} , at Visit 1 only)	x	x ⁶	x
Pregnancy test (women of childbearing potential only)	x ⁷	x ^{1,8}	x ⁸
Urinalysis	x	x ¹	x
Urine drug screen	x	x ¹	
Alcohol breath test	x	x ¹	
PK/Clinical efficacy			
Plasma dasiglucagon/GlucaGen		x ⁹	
Plasma glucose		x ¹⁰	
Other assessments			
Antibodies against dasiglucagon/GlucaGen		x ¹	x ¹¹
Plasma insulin		x ¹²	
Trial material			
Administration of trial product (during hypoglycemic clamp procedure)		x	

¹Prior to the start of the insulin-induced hypoglycemic procedure.

²Only check of dosing day exclusion criteria and changes between screening visit and Visit 2.

³Prior to the start of the insulin-induced hypoglycemic procedure (within 30 minutes), and at 30, 90 and 300 minutes after dosing. The actual time of the assessment should not deviate from the nominal time by more than ±10 minutes.

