9.2 Trial subjects

9.2.1 *Analysis samples*

For presentation of data and reporting of the statistical analyses, the following analysis samples will be used, depending on the context:

- Safety analysis set (SAS): All randomized subjects who received at least one dose of trial medication.
- Full analysis set (FAS): All randomized subjects who received at least one dose of trial medication.
- Per protocol (PP) set: All subjects of the FAS for whom no relevant protocol deviations were documented. This sample will primarily be used for sensitivity analysis.

The analysis of the primary endpoint and secondary endpoints will be based on the FAS. A secondary analysis of the primary endpoint will be based on the PP set. All safety analyses will be based upon the SAS.

The decision regarding whether a protocol deviation is relevant or not for the exclusion of subjects from the PP set will be made case-by-case in a data review meeting prior to treatment unmasking and database lock (see Section [9.2.3](#)).

9.2.2 *Disposition of subjects*

Subject disposition will be tabulated including the number of screened subjects, screening failures, subjects exposed to trial product, subjects completing the trial and subjects in each analysis set.

Subjects withdrawn from the trial will be listed including the primary reason for withdrawal.

9.2.3 *Protocol deviations*

Before data are released for statistical analysis, a treatment-masked review of all data will take place to identify protocol deviations that may potentially affect the results. This review will be performed without revealing to which trial product the subjects were assigned. The masking of the trial products will be maintained for everyone involved in allocating subjects to the analysis sets until data are released for statistical analysis.

Furthermore, spurious outliers will be evaluated. In addition, protocol deviations that may potentially affect the results will be identified and it will be evaluated if subjects and/or data should be excluded from the analysis. Protocol deviations will be classified as minor or major in a consistent way. Major deviations from the protocol may lead to the exclusion of a subject from the PP set.

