9.7 Safety analyses

9.7.1 Adverse events

AEs will be coded using the latest available version of the MedDRA, the version of which will be provided in the clinical trial report. AE summary tables will include the number and percentage of subjects who experienced AEs summarized by system organ class and preferred term.

Germany only: The AE summary for AEs related to insulin glulisine (Apidra[®]) will be presented as an appendix to the clinical trial report, as insulin glulisine (Apidra[®]) is only defined as an IMP in Germany.

An overall summary table will be provided showing the number and percentage of subjects with any:

- TEAE
- Severe TEAE
- Serious TEAE
- Drug-related TEAE
- Drug-related severe TEAE
- Drug-related serious TEAE
- TEAE leading to withdrawal
- TEAE with outcome death
- AESI

Refer to Section 7.2.1 for the definition of TEAEs.

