10.10 Duration of the trial

The maximum duration of the trial for each subject will be up to 63 days (including up to 30 days for screening and up to 33 days until the follow-up visit).

The trial will be closed when all subjects have completed Visit 3.

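### TEAEs are defined from informed consent rather than from dosing, so pre-dose screening and clamp events in later-dosed subjects enter the by-arm TEAE tables (should-fix)

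*Protocol*

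**What the plan says.** Section 7.2.1.1 of the protocol gives the definition: "TEAEs are events that occur from the first trial-related activity after the subject has signed the informed consent form until the end". The end meant is that of follow-up after treatment. The sentence before it reads "In this trial, only treatment-emergent adverse events (TEAEs) will be collected and reported". Section 7.2.1.2 sets the collection window for all AEs with the same start and end: "All events meeting the definition of an AE must be collected and reported from the first trial related activity" after consent.

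Section 9.7.1 lists nine rows for the overall AE summary: any, severe and serious TEAE; drug-related, drug-related severe and drug-related serious TEAE; TEAE leading to withdrawal; TEAE with fatal outcome; and AESI. It gives no definition of its own: "Refer to Section 7.2.1 for the definition of TEAEs". It also plans tables of AEs by system organ class and preferred term.

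Safety analyses use the safety analysis set of section 9.2.1: "All randomized subjects who received at least one dose of trial medication".

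On timing, section 8.2.1 says "Visit 1 will take place between 3 and 30 days before Visit 2". Section 8.2.3 places randomization on Day 1 before the insulin procedure, and section 8.2.3.1 has the injection follow once glucose is in range. Section 7.2.2 makes hypoglycemia an AE, with a threshold of 70 mg/dL in general and 45 mg/dL from the start of the clamp until 45 minutes after dosing. It foresees values below 45 mg/dL before the injection.

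**The concern.** A treatment-emergent event is normally one that starts or worsens once treatment has been given. Here treatment is one injection at a recorded minute, and the definition does not refer to it. The term therefore covers every AE collected, including those that the study drug cannot have caused.

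Such events are foreseeable in this design. Subjects with insulin-treated type 1 diabetes have their usual insulin washed out, may receive insulin glulisine overnight, and are then driven to hypoglycemia by infusion. Section 8.2.3.1 provides for an extended run-in, a second attempt and a rescheduled visit, so some subjects may undergo more than one induction before dosing.

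At stake is the reading of the main safety tables. Rates in each arm would include a background that precedes treatment, and differences between active drug and placebo would look smaller than they are. In a safety table, dilution is the unconservative direction. In the hypoglycemia row, pre-dose clamp lows and post-dose lows would be merged.

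**Working it through.** The plan states no figure to reproduce, because this is a question of definition. The check has three steps.

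**1. Does any text limit TEAEs to post-dose onset?**

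| Item | Where | Start of window |
|---|---|---|
| AE collection | 7.2.1.2 | first trial-related activity after consent |
| TEAE | 7.2.1.1 | the same |
| TEAE in the analysis | 9.7.1 | refers back to 7.2.1 |
| AESI | 7.2.1.1 | post-dose |

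Only the AESI definition is tied to dosing. The general AE definition in 7.2.1.1 speaks of a subject given an IMP, which fits poorly with a window opening at consent, but the TEAE sentence states the consent start outright. TEAE therefore equals every collected AE.

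**2. How much of the window is pre-dose?**

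Section 10.10 gives the longest course as "including up to 30 days for screening and up to 33 days until the follow-up visit", 63 days in all.

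- Longest course: 30 / 63 = 47.6%.
- Three-day screening and a Day 28 visit: 3 / (3 + 28) = 9.7%.

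These are shares of calendar time, not of events.

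**3. What does a pre-dose background do to a contrast?**

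Let p1 and p0 be the post-dose probabilities of at least one event on active drug and placebo, and q a pre-dose probability equal in both arms. Treat pre-dose and post-dose events as independent. Under the stated definition:

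- rate in an arm = 1 − (1 − q)(1 − p)
- risk difference = (1 − q)(p1 − p0)

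The difference shrinks by exactly 1 − q and the ratio moves toward 1. All values of p1, p0 and q below are assumptions; none is in the documents.

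| q | Rates if p1 = 60%, p0 = 20% | Difference (points) | Ratio | Rates if p1 = 30%, p0 = 10% | Difference (points) | Ratio |
|---|---|---|---|---|---|---|
| 0 | 60 / 20 | 40 | 3.0 | 30 / 10 | 20 | 3.0 |
| 5% | 62 / 24 | 38 | 2.6 | 33.5 / 14.5 | 19 | 2.3 |
| 10% | 64 / 28 | 36 | 2.3 | 37 / 19 | 18 | 1.9 |
| 20% | 68 / 36 | 32 | 1.9 | 44 / 28 | 16 | 1.6 |
| 40% | 76 / 52 | 24 | 1.5 | 58 / 46 | 12 | 1.3 |

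The q = 0 row is what a dose-anchored definition would show.

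**The case against.** The strongest reply is that the reach is limited, and most of it stands.

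- **Not every row is affected.** AESIs are post-dose by definition. The three drug-related rows depend on the investigator's causality grading, and an event before the injection gives little ground for a related grade. A subject withdrawn before dosing is not in the safety set, so the withdrawal row is barely touched, and the same reasoning covers the fatal-outcome row.
- **Pre-dose events are restricted.** Section 5.5 keeps a subject from dosing after clinically significant illness in the previous 4 weeks, which covers 28 of the 30 possible screening days. It does the same for glucose below 50 mg/dL in the previous 24 hours or below 60 mg/dL in the 5 hours before the procedure. Conditions found at screening are not AEs. The restriction is partial: one reschedule is allowed, minor events remain, and glucose lows outside these limits can still count.
- **The planned hypoglycemia is not itself an AE.** The clamp targets 55 mg/dL, and only a fall below 45 mg/dL counts.
- **The label is about timing, not cause.** A reader might infer that the plan attributes clamp events to dasiglucagon. It does not: causality is a separate field, and at German sites, where insulin glulisine is also an IMP, causality to the insulin is recorded separately. That status might justify a start at the insulin infusion there, but not at consent.
- **The SAP may refine details.** Section 9 allows this. But the protocol does not leave the point open: it fixes a definition and ties the analysis to it. A SAP that used dose onset would contradict it.

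A reader might also take 48% as the share of TEAEs that would be pre-dose, or conclude that the nausea contrast would be badly diluted, since the introduction names nausea both as a symptom of hypoglycemia and as the drug's most frequent systemic AE. The documents support neither. The 48% is the maximum calendar share. No pre-dose nausea rate is given, and a diagnosis is recorded where possible, so a clamp low would usually be recorded as hypoglycemia.

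**Conclusion.** The definition is wrong as written and should be corrected. It makes treatment-emergent mean every AE collected, and it carries new pre-dose events of later-dosed subjects into the any, severe and serious TEAE rows and the system organ class and preferred term tables.

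The effect is inflation in all arms and dilution of contrasts by 1 − q on the difference scale. Its size cannot be fixed because the documents give no pre-dose event rate; it is small if q is near 5% and material if q is near 40%. The formula assumes equal pre-dose rates across arms, which randomization supports on average, and independence of pre-dose and post-dose events.

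A reader might infer a bias for or against one arm, or a threat to the trial's conclusions. Neither follows: the background is expected to be balanced, and the primary endpoint, the testing hierarchy and power do not use TEAEs. The sample size rests on the size of the safety database, but that sets the number exposed; no AE contrast is powered. The point is a should-fix.

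**What to change.** - In section 7.2.1.1, define a TEAE as an AE with onset, or worsening, at or after IMP administration through Visit 3. State that IMP here means the randomized study drug, so that insulin glulisine at German sites does not move the start.
- Replace the sentence that restricts collection to TEAEs, since with the new definition it would stop the collection of pre-dose AEs. AEs should still be collected from consent.
- In section 9.7.1, state that the overall summary and the system organ class and preferred term tables use TEAEs. The latter now refer to AEs, so changing the definition alone would leave them as they are.
- Add one table of pre-dose AEs, split into screening and clamp before dosing.

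The data are already planned: section 7.2.1.2 records date and time of AE onset, and section 8.2.3.1 records the time of IMP administration. The cost is wording in two sections and one extra table.
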